**PROTOCOL SUMMARY**

Study Title	Evaluation of the GORE® EXCLUDER® Thoracoabdominal Branch Endoprosthesis in the Treatment of Thoracoabdominal and Pararenal Aortic Aneurysms
Protocol Number	AAA 17-01
IDE Number	G150071
Sponsor	W. L. Gore & Associates, Inc. [REDACTED] [contact]
Study Design	Prospective, non-randomized, multicenter study with two independent arms: 
 
• Primary Study Arm – TAAA requiring only TAMBE System. Hypothesis-driven analysis.
 
• Secondary Study Arm – TAAA requiring TAMBE System and CTAG Device(s). Non-hypothesis-driven analysis.
 

Study Objective	Assess the safety and effectiveness of the TAMBE Device in the treatment of thoracoabdominal and pararenal aortic aneurysms
Co-Primary Study Endpoints	
 
1. Uncomplicated Technical Success / Procedural Safety Co-Primary Endpoint A composite of the following events: 
 
• Device Technical Success at the time of the index endovascular procedure
 
• Procedural Safety events within 30 days of index procedure:
 
 
 
2. Clinically Significant Reintervention / Lesion-Related Mortality Co-Primary Endpoint (12 months post-treatment) 
 
• Clinically Significant Reintervention (using protocol definition)
 
• Lesion-Related Mortality
 
 
 

Subject Population	Subjects with thoracoabdominal or pararenal aortic aneurysms requiring treatment Primary Study Arm: Adapted Crawford Type IV TAAA and Pararenal aneurysms (n= 102)

	
Secondary Study Arm: Adapted Crawford Type I-III (n= 20 - 100)
 
Continued Access (Primary Study Arm): Adapted Crawford Type IV TAAA and Pararenal Aneurysms (n=up to 65)

Number of Implanted Subjects	Minimum: 122 implanted subjects, Maximum: 202 implanted subjects with up to 65 additional subjects implanted in Continued Access (Primary Study arm).
Number of Sites	Up to 45 sites in the United States and Europe
Coordination PI	[REDACTED]
Brief Inclusion Criteria	
 
• Aortic aneurysm involving the visceral vessels requiring treatment defined as at least one of the following: 
 
○ Fusiform aneurysm diameter <math>\geq</math> 5 cm
 
○ Saccular aneurysm (no diameter requirement)
 
○ Rapid aneurysm growth (<math>\geq</math> 5 mm in one year)
 
 
 
• An Informed Consent Form signed by Subject or legal representative
 
• Appropriate aortic anatomy to receive the TAMBE Device defined as all of the following: 
 
○ For the TAMBE Aortic Component, proximal aortic landing zone diameters between 22 -34 mm
 
○ Proximal seal zone <math>\geq</math> 20 mm in length
 
 
 

Brief Exclusion Criteria	
 
• Prior open, aortic surgery of the ascending aorta or aortic arch
 
• Myocardial infarction or stroke within 1 year of treatment (staged or index procedure)
 
• Previous instance of Heparin Induced Thrombocytopenia type 2 (HIT-2) or known hypersensitivity to heparin
 
• Renal insufficiency (creatinine value <math>></math> 1.8 mg/dL, GFR <math><</math> 30, or patient undergoing dialysis)
 

Expected Time to Complete Enrollment	
Primary Study Arm Subject Accrual: 27-32 months
 
Follow-up – 5 years from last subject enrollment

Brief Schedule of Events	
Screening
 
Pre-Treatment
 
Treatment
 
Discharge
 
Follow-up (30 day, 3, 6, 12 months and annually thru 5 years)

## 1. Introduction

This Statistical Analysis Plan (SAP) describes the statistical analyses planned to address the objectives of the AAA 17-01 clinical study. This SAP summarizes the analyses that will be performed to determine the safety and effectiveness of the Thoracoabdominal Branch Endoprosthesis (TAMBE) Device when used for endovascular repair of thoracoabdominal and pararenal aortic aneurysms in subjects with appropriate anatomy. This SAP outlines tables, figures, and listings that are included in reports for the AAA 17-01 clinical study.

### 1.1 Study Success

Study success will be defined as rejecting the null hypotheses from both the Uncomplicated Technical Success Endpoint and the Clinically Significant Reintervention endpoints.

## 2. Study Design Overview

This will be a prospective, non-randomized, two-armed, multicenter study conducted at up to forty-five (45) Clinical Investigative Sites (referred to as “sites” in the remainder of this document) in the United States and Europe. A minimum of 122 subjects, up to a potential maximum of 202 subjects, will be implanted with the TAMBE Device across two independent study arms as described below.

- Primary Study Arm – Hypothesis-driven analysis, Thoracoabdominal aneurysms (TAAAs) which are anatomically suitable for treatment with the TAMBE Device and do not require proximal extension with a CTAG Device (N=102). This arm will be limited to pararenal aortic aneurysm and adapted Crawford Type IV TAAAs.
- Secondary Study Arm – Non hypothesis-driven analysis, TAAAs which are anatomically suitable for treatment with the TAMBE Device and would require proximal extension with CTAG Device(s). This arm will include adapted Crawford Type I-III TAAAs. (N=20-100 Subjects)

Up to 65 additional subjects may be implanted in the Continued Access Phase under the Primary Study Arm only. All sites will be allowed to enroll in the Continued Access Phase, and all sites and subjects will be treated and followed in the same manner as the Core Clinical Investigation.

- The reduced profile VBX Device cohort (a subset of the Continued Access phase) will follow the TAMBE protocol: all primary, secondary, and other endpoints will be collected for these subjects as per protocol in the same manner as for the other cohorts. The Target Vessel Technical Success of the reduced profile VBX Device for each vessel will also be assessed.
- To assess the compatibility of reduced profile VBX Device as a side branch component in conjunction with the TAMBE Aortic Component (AC), the following endpoints will be summarized at a subject level:
  - Uncomplicated Technical Success at Index Procedure
  - Procedural Safety data through 30-day follow-up
  - Summary of AEs through 30-day follow-up including Type Ic and IIc Endoleaks

2.1 Objectives

2.1.1 Primary Objective(s)

The primary objective of the study is to determine whether the GORE® EXCLUDER® Thoracoabdominal Branch Endoprosthesis is safe and effective in the treatment of thoracoabdominal and pararenal aortic aneurysms.

The study will utilize separate, independent hypothesis-driven analyses in order to make this determination in the study’s target population of pararenal aortic aneurysm subjects and adapted Crawford Type IV thoracoabdominal aneurysm subjects.

Gore recognizes that the TAMBE Device, in combination with proximal CTAG Device extension, may have applicability to Crawford Type I-III thoracoabdominal aneurysm subjects. Hypothesis-driven assessments will not be performed in this secondary study arm population with device performance characterized for potential future applications.

2.1.2 Secondary Objective(s)

There are no Secondary Objectives specified for this study.

2.2 Design Summary

AAA 17-01 is a prospective, non-randomized, multi-center trial that will compare the Uncomplicated Technical Success / Procedural Safety and Clinically Significant Reintervention / Lesion Related Mortality co-primary endpoints to pre-specified performance goals. A minimum of 122 subjects and a maximum of 202 subjects will be enrolled and implanted across both sub-groups; 102 Subjects within the Primary Study Arm and between 20 and 100 Subjects within the Secondary Study Arm, with a minimum requirement of 20 combined adapted Crawford Type I and Type II aneurysms. Subjects will be evaluated through hospital discharge and return for follow-up visits at one (1), three (3), six (6), 12, 24, 36, 48 and 60 months. This is a confirmatory study.

2.3 Study Endpoints

2.3.1 Primary Endpoint(s)

There are two Co-Primary Endpoints used in this study: Uncomplicated Technical Success / Procedural Safety and Clinically Significant Reintervention / Lesion Related Mortality. A hypothesis test will be conducted on each Co-Primary Endpoint.

1. Uncomplicated Technical Success / Procedural Safety Co-Primary Endpoint (evaluated through 30 days post procedure)

**Table 1** displays the components for the Uncomplicated Technical Success Primary Endpoint, along with their definitions, time each item is evaluated and the final source data for each item. Definitions provided are referenced from the Clinical Protocol, Section 3.3.

**Table 1: Summary of Uncomplicated Technical Success Primary Endpoint**

Outcome	Definition (per Clinical Protocol Section 3.3)	Endpoint Time Evaluated	Final Source Data
Uncomplicated Technical Success			
Successful access and delivery	
All Gore devices are successfully tracked from the access site to the intended implantation site and released from the deliver catheter successfully without the need for unanticipated corrective intervention related to delivery.
	TAMBE Device Index procedure	Site data
Successful and accurate deployment	
Deployment of all required endovascular device components in the planned location:
 
 
- Patency of required aortic endovascular grafts with absence of device deformations (e.g., kinks) requiring unplanned placement of a non-TAMBE device component* within the endovascular graft;
 
- Patency of all branch devices with absence of device deformations (e.g., kinks) requiring unplanned placement of any non-TAMBE device component* within the branches**;
 
 
* TAMBE components include the aortic component, distal bifurcated component, iliac extenders, contralateral legs, VBX component and CTAG Device.
 
**Implantation of bare metal stents to smooth the transition from the VBX to the uncovered branch vessel will not count against technical success if the procedure otherwise meets the definition of technical success. Use of non-TAMBE devices to correct iatrogenic complications in the treated aorta or branch vessels would be considered technical failures.
	TAMBE Device Index procedure	Site Reported and CEC Adjudication 
Successful withdrawal	Successful withdrawal of the delivery systems, without a need for corrective intervention related to withdrawal	TAMBE Device Index procedure	Site data
Procedural Safety			

Outcome	Definition (per Clinical Protocol Section 3.3)	Endpoint Time Evaluated	Final Source Data
Aortic Rupture	Rupture in the stented segment of the aorta verified with direct observation or CT scan	30 days	CEC adjudication
Lesion-related mortality	Defined as all deaths during hospitalization for index endovascular procedure and within 30 days of the index endovascular procedure or any secondary procedures due to the treated pathology, or the effectiveness of the endovascular repair (e.g., procedures to treat retrograde dissections, losses of patency, losses of device integrity, endoleaks, migrations, aortic expansions, aortic ruptures) and any deaths related to the treated pathology or endovascular graft (e.g., aneurysm rupture, retrograde dissection leading to fatal cardiac tamponade), unless evidence is available to demonstrate that the death is not lesion related	30 days or in-hospital for index endovascular procedures	
Permanent paraplegia	Paraplegia secondary to spinal cord ischemia identified within 30 days of the index endovascular procedure combined with spinal cord ischemia scale grade of "3" at the one-month follow-up visit. The grading system for spinal cord ischemia is described in TEVAR reporting standards	Event reported within 30 days of endovascular procedure without resolution at one month follow-up	
Permanent paraparesis	Paraparesis secondary to spinal cord ischemia identified within 30 days of the index endovascular procedure combined with spinal cord ischemia scale grade of "2" at the one-month follow-up visit. The grading system for spinal cord ischemia is described in TEVAR reporting standards	Event reported within 30 days of endovascular procedure without resolution at one month follow-up	
New onset renal failure requiring dialysis	New onset sustained renal failure identified within 30 days of the index endovascular procedure, combined with need/requirement for dialysis at the one month follow-up visit	Event reported within 30 days of endovascular procedure without resolution at one month follow-up	
Severe bowel ischemia	Bowel ischemia resulting in bowel resection or fatal outcome	30 days	
Disabling stroke	Stroke was assessed using the Modified Rankin Scale. Stroke identified as having occurred within 30 days of the index endovascular procedure, combined with mRS $\geq 2$ with an increase from baseline of at least one grade at 90 days  Modified Rankin Score was completed by an allied health staff member who successfully completed mRS certification or licensed medical professional	120 days (30 days for Stroke Events, plus 90 days for mRS measurements)	

As part of successful and accurate deployment, the CEC will adjudicate use of non-TAMBE devices to correct iatrogenic complications in the treated aorta or branch vessels.

2. Clinically Significant Reintervention / Lesion Related Mortality Co-Primary Endpoint (12 months post-treatment)

**Table 2** contains the definition, endpoint time evaluated, and the final source data for the components of the Clinically Significant Reintervention / Lesion Related Mortality Co-Primary Endpoint. This endpoint is evaluated at 12 months post-treatment.

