4.1 Study Collection Intervals

Subjects will be asked to return for follow-up visits at one (1), three (3), six (6), 12, 24, 36, 48, and 60 months post-treatment. At each follow-up visit, subjects will undergo an evaluation for adverse events.

Table 4: Schedule of Events

	Pre-treatment (Screening)	Treatment	Hospital Discharge	One Month	Three Months	Six Months	Annually through 5 Years
Informed Consent	X						
Demographics and Medical History	X						
Risk Scales (ASA, NYHA, SVS)	X						
Physical examination	X		X	X	X	X	X
Adverse Events	X	X	X	X	X	X	X
Medication Review	X		X	X	X	X	X
Modified Rankin Scale a,b	X		X	X	X if applicable	X	
Spinal Cord Ischemia Scale a	X		X	X		X	

NIH Stroke Scale c	X		X If applicable				
SF-36 Questionnaire	X			X	X	X	X
Serum Creatinine Concentration	X		X	X	X	X	X
Spiral CTA (contrast) d	X			X		X	X
Spiral CT (non-contrast)				X		X Optional	X Optional
Completion Angiogram		X					
Magnified Branch Visualization		X					
Abdominal Ultrasound	X		X	X	X	X	X
Multiplanar Device Radiographs (X Ray)				X		X	X

a If subject is unable to return to the site for a follow-up visit, they may be contacted by telephone to evaluate the Modified Rankin Scale and Spinal Cord Ischemia Scale.

b For subjects suspected of having a stroke event within 30 days following the index endovascular procedure an additional mRS score should be completed at 90 days following the suspected stroke event but no greater than 120 days post index endovascular procedure.

c NIH Stroke Scale should be performed for any subject suspected of having a stroke event that undergoes the treating site's stroke protocol during the study interval from the initiation of the index endovascular procedure until discharge. The scale should be performed as soon as possible after learning of the suspected event and again at the time of discharge.

d CTA of chest/abdomen/pelvis at Screening. CTA of abdomen and pelvis at all follow-up visits, except for Secondary Study Arm Subjects who must have a CTA of chest/abdomen/pelvis at all visits. MRA may be used in place of CTA during follow-up if the Subject is contraindicated for CTA.

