## 5. Statistical Analyses

### 5.1 Analysis Populations

The following populations will be used in various analyses of the data collected in the AAA 17-01 study:

1. All Enrolled Subjects - This population will consist of all enrolled Subjects. A patient is considered enrolled into the study once the Main informed consent has been signed and dated.
2. All Enrolled and Implanted Subjects - This population will consist of all enrolled and implanted Subjects. A patient is considered enrolled into the study once the Main informed consent has been signed and dated, and successfully implanted with the study device (TAMBE in the primary arm, CTAG + TAMBE in the secondary arm).
3. Uncomplicated Technical Success Eligible Population (each study arm) [Per protocol population] - This population will consist of enrolled and implanted Subjects with a follow-up visit at or after 30 days following initial TAMBE Device implant procedure. Additionally, any Subjects with an eligible technical success event, as defined in **Section 2.3.1**, even if they did not complete a follow-up visit at or after 30 days following initial procedure, will be included.
4. Clinically Significant Reintervention / Lesion Related Mortality Population (each study arm) - This population will consist of enrolled and implanted Subjects that have completed the 12 month analysis window. Additionally, any Subjects with an eligible clinically significant reintervention event, as defined in **Section 2.3.1**, even if they did not complete the necessary follow-up visit or imaging to otherwise be included in the population, will be included.
5. Secondary Effectiveness Populations (each study arm, each endpoint) - These populations will consist of enrolled Subjects with an evaluable result for the specific variable.
6. Reduced Profile VBX Population – This population will consist of the subjects in the Continued Access Phase who had been implanted with at least one reduced profile VBX device.

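### In the Primary Study Arm, defined as not needing CTAG, Table 1 still counts CTAG as a TAMBE component, so an unplanned CTAG escapes the two device-based technical-failure clauses

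*Combined protocol and SAP*

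**What the plan says.** **Arms.** The Protocol Summary separates a Primary Arm that needs the TAMBE System only from a Secondary Arm that needs the TAMBE System and CTAG. SAP Section 2 describes Primary Arm aneurysms as ones that "do not require proximal extension with a CTAG Device (N=102"), and Section 3.1 agrees. Section 5.1, item 2, defines implanted subjects as "successfully implanted with the study device (TAMBE in the primary arm, CTAG + TAMBE in the secondary arm"). Only the Primary Arm is tested (Section 5.4).

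**Technical success.** Under successful and accurate deployment, Table 1 has two clauses that turn on the type of device used:

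- Deformation. For the aortic graft, the failure is a deformation "requiring unplanned placement of a non-TAMBE device component* within the endovascular graft". The asterisk leads to the component list.
- Iatrogenic complications. "Use of non-TAMBE devices to correct iatrogenic complications in the treated aorta or branch vessels would be considered technical failures".

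The list behind both clauses is: "TAMBE components include the aortic component, distal bifurcated component, iliac extenders, contralateral legs, VBX component and CTAG Device". It makes no distinction between arms. Footnote 1 to Table 1 gives the CEC the task of adjudicating non-TAMBE devices used for iatrogenic complications, and mentions no other device use.

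Table 1 also has criteria that do not depend on the type of device. Components must be deployed where planned, and no corrective intervention may be needed in connection with delivery (if unanticipated) or with withdrawal. Delivery and withdrawal are scored from site data.

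**The concern.** In the arm sections CTAG is a separate device, and not needing it is what places an aneurysm in the Primary Arm. In the endpoint table CTAG is part of the system under test. Listing it makes sense in the Secondary Arm, where its use is planned. In the Primary Arm, its unplanned use to correct a deformed graft or an iatrogenic aortic complication means that the TAMBE System alone did not suffice, which is the kind of event the two clauses were written to catch.

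At stake is the first co-primary endpoint. It is an uncontrolled comparison with an 80% performance goal, and study success requires both co-primary nulls to be rejected (Section 1.1). A scoring rule that can turn a failure into a success, but never the reverse, should be deliberate and visible.

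**Working it through.** **1. Inputs.** Performance goal 0.80 (Section 2.4); one-sided exact Clopper-Pearson bound at alpha 0.05 (Section 5.4); 102 implanted and 86 expected evaluable subjects (Section 2.6).

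**2. The plan's own figures.** 86 / (1 − 0.15) = 101.2, rounded up to 102, which matches. The assumed true success rates are not in the public text. Solving backwards with n = 86:

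- A true rate of 0.80 against 0.68 (pass at 66 or more) gives the stated 81.48% power.
- A true rate of 0.923 against 0.80 (pass at 76 or more) gives the stated 93.41%.

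The stated powers are therefore consistent with this test, though not independently reproduced. This point changes none of them.

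**3. How Table 1 scores an index-procedure event in the Primary Arm.**

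| Event | Corrected with an off-list device | Corrected with an unplanned CTAG |
|---|---|---|
| Graft delivered, placed as planned, delivery system withdrawn cleanly; graft then found deformed | Failure (deformation clause) | Not a failure on the wording of any deployment, delivery or withdrawal criterion |
| Iatrogenic complication in the treated aorta | Failure (iatrogenic clause); covered by CEC footnote | Neither clause nor the CEC footnote applies; may fail if the correction relates to delivery or withdrawal |
| Component not in its planned location | Can fail on planned location | Can fail on planned location |

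The gap is in the first two rows. The third is scored alike whichever device is used.

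**4. How much one subject matters.** With x successes in n, the lower bound is the 5% quantile of Beta(x, n − x + 1).

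| Successes | Lower bound | Exceeds 0.80? |
|---|---|---|
| 76/86 | 0.811 | Yes |
| 75/86 | 0.797 | No |
| 89/102 | 0.805 | Yes |
| 88/102 | 0.794 | No |

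At the limit, rescoring a single subject reverses the conclusion.

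**5. Illustration only.** Let b be the proportion of Primary Arm subjects with an unplanned CTAG that falls in the gap. The documents give no value, so 1% to 3% is assumed. Assume also that these subjects otherwise succeed, and that the success rate is exactly 0.80 when they count as failures. Scoring them as successes gives an apparent rate of 0.80 + b, and the chance of passing is P(X ≥ c) for X ~ Binomial(n, 0.80 + b), where c is the pass mark.

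| b | n = 86, c = 76 | n = 102, c = 89 |
|---|---|---|
| 0 | 3.0% | 3.9% |
| 1% | 4.8% | 6.4% |
| 2% | 7.6% | 10.2% |
| 3% | 11.5% | 15.5% |

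**The case against.** **The plan may be asking whether the sponsor's device family suffices.** Unplanned VBX components or iliac extenders are exempt too, so exempting CTAG could be consistent. But those parts belong to the system in both arms. CTAG is the one listed component that the arm definitions set apart from the TAMBE System, and no reason is given for exempting it in the arm that excludes its need.

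**Other criteria may catch the event.** This stands in part. The criteria in Table 1 that do not depend on device type will catch some cases, and a verified rupture of the stented aorta is a separate safety event. It would be wrong to say that an unplanned CTAG is never a technical failure. The second co-primary counts a kink, collapse or seal compromise that needs a further stent or stent-graft (Table 2), but it tests a different hypothesis and does not say whether index-procedure events count.

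**The error rates presuppose the stricter endpoint.** This stands. Under the plan's own definition the attained alpha at n = 86 is 3.0%. The documents do not show which definition the 80% goal was set on, and at b = 1% with n = 86 the illustrative figure stays below 5%.

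**The governing text may lie elsewhere.** Clinical Protocol Section 3.3 is not in the available text and SAP Section 5.6 is redacted, so a rule may exist there. Table 1, however, states that it gives the Section 3.3 definitions, and it has no arm-specific rule.

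**Conclusion.** The point holds as an inconsistency between the arm definition and the endpoint definition. In the tested arm, an unplanned CTAG for an aortic-graft deformation or an iatrogenic complication in the treated aorta is exempt from both device-based clauses, and the CEC footnote does not reach it. Relative to scoring it like an off-list device, the effect can only favour the device. Its size is unknown: one subject can decide a result at the limit, and the percentages above depend wholly on assumed rates and on taking the stricter scoring as the truth.

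Three stronger readings are not supported:

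- **That the subject moves to the Secondary Arm and leaves the denominator.** A reader might infer this from the device wording in Section 5.1. No text reassigns anyone, and Section 2 also fixes the arms by anatomy: "This arm will be limited to pararenal aortic aneurysm and adapted Crawford Type IV TAAAs" for the Primary Arm and "This arm will include adapted Crawford Type I-III TAAAs" for the Secondary. An unplanned device does not change the aneurysm type.
- **That follow-up imaging would be inadequate.** Table 4, footnote d, sets abdomen and pelvis CTA as the follow-up rule "except for Secondary Study Arm Subjects who must have a CTA of chest/abdomen/pelvis at all visits". Nothing shows that this would miss an endpoint event, and Section 4 makes the schedule a minimum.
- **That an aortic injury above the graft shows the same contrast.** Such an injury is not clearly within either clause, whichever device is used.

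**What to change.** 1. In the Table 1 component footnote, count CTAG as a TAMBE component only in the Secondary Arm, where its use is planned.
2. In the Primary Arm, apply the existing deformation and iatrogenic-complication clauses, and CEC footnote 1, to an unplanned CTAG exactly as to any non-TAMBE device. Failing every unplanned CTAG regardless of reason would go too far, because non-TAMBE devices fail only for those two reasons.
3. Report the number of Primary Arm subjects affected, and give the result under the present scoring as a sensitivity analysis.
4. Optionally, state in Section 5.1 that the arm is fixed by the pre-procedure plan. This removes an ambiguity but is not needed for the main change.

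The cost is wording in Table 1 and its footnotes, matched in the protocol definition, and CEC review of any such cases. No new data are needed if, as expected, the devices used at the index procedure are already recorded. The downside for the sponsor is that the success rate may be slightly less favourable.

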**Table 2: Summary of Clinically Significant Reintervention / Lesion Related Mortality Co-Primary Endpoint**

Outcome	Definition (per Clinical Protocol Section 3.3)	Endpoint Time Evaluated	Final Source Data
Clinically Significant Reintervention			
Clinically-Indicated Condition	An untreated device seal zone endoleak, target-lesion growth (> 5 mm in maximum diameter) or post-treatment TAAA rupture without reintervention at the 12 Month window follow-up visit	12 mo f/u visit	Core Lab (aneurysm size and endoleak) CEC Adjudication (TAAA rupture) Site Data (reintervention)
Device Effectiveness	A compromise of a device seal zone or loss of device integrity (e.g., device kink or collapse) requiring placement of an additional stent or stent-graft	12 mo f/u visit	CEC adjudication
Subject Safety	Total occlusion of a device component, use of a bypass graft or the performance of an open conversion in order to maintain bodily vessel function	12 mo f/u visit	
Complicated Device System Prophylaxis	Any device-related intervention requiring hospitalization, or extension of hospitalization, of three days or more	12 mo f/u visit	
Lesion-related mortality			
Lesion-related mortality	All deaths during hospitalization for index endovascular procedure and within 30 days of the index endovascular procedure or any secondary procedures due to the treated pathology, or the effectiveness of the endovascular repair (e.g., procedures to treat retrograde dissections, losses of patency, losses of device integrity, endoleaks, migrations, aortic expansions, aortic ruptures) and any deaths related to the treated pathology or endovascular graft (e.g., aneurysm rupture, retrograde dissection leading to fatal cardiac tamponade), unless evidence is available to demonstrate that the death is not lesion related	12 mo f/u visit	CEC adjudication

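### Early deaths shown to be not lesion related are not Procedural Safety failures and normally leave the denominator, and the plan does not say that procedure-caused deaths must stay in

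*Combined protocol and SAP*

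**What the plan says.** The Protocol Summary describes the safety half of the first co-primary endpoint as "Procedural Safety events within 30 days of index procedure". SAP Section 2.3.1, Table 1, lists its components.

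The mortality row has three parts:
- **Timing.** The opening words are "Defined as all deaths during hospitalization for index endovascular procedure and within 30 days of the index endovascular procedure", and the row extends to deaths around secondary procedures.
- **Cause.** It adds "any deaths related to the treated pathology or endovascular graft".
- **Release.** It ends "unless evidence is available to demonstrate that the death is not lesion related".

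Table 2 (second co-primary) and the aneurysm-related mortality row of Table 3 carry the same release clause. Tables 1 to 3 list no all-cause and no procedure-related mortality endpoint.

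Some fatal events have their own rows in Table 1: "Bowel ischemia resulting in bowel resection or fatal outcome" and "Rupture in the stented segment of the aorta verified with direct observation or CT scan".

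Section 5.1 limits the analysis population for this endpoint to "enrolled and implanted Subjects with a follow-up visit at or after 30 days following initial TAMBE Device implant procedure", plus subjects who have an endpoint event without that visit. Sections 2.4 and 5.4 test the endpoint against a goal of 80% with a one-sided exact Clopper-Pearson bound at alpha 0.05.

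**The concern.** The component sits under Procedural Safety, but its exit test asks about the lesion. The cause limb just before it names the pathology and the graft, not the procedure. Lesion related has no definition apart from this sentence. A perioperative cardiac death is the clearest case: the procedure can cause it, yet it can be documented as not arising from the aneurysm or the graft.

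The remaining components are a weak net for such a death. Paraplegia, paraparesis and dialysis depend on status at the one-month visit, and disabling stroke depends on a 90-day mRS. Table 1 does not say how a subject who dies first is scored on these. Mortality is therefore the main component that would register an early death, and it is the one with the release clause.

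A released death then meets Section 5.1. With no event and no visit at or after 30 days, the subject leaves the analysis. Any error from this runs one way, in favour of the device, on the endpoint that carries the safety claim.

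**Working it through.** **1. The plan's own figures.** Inputs from Sections 2.4, 2.6 and 5.4: goals 0.68 and 0.80, one-sided exact test, alpha 0.05, 102 implanted, 86 evaluable after 15% loss (86/0.85 = 101.2, rounded up to 102). The pass mark r is the smallest count with P(X ≥ r | n, goal) ≤ 0.05.
- Goal 0.68, n = 86: r = 66. Power at a true rate of 0.80 is 0.8148, which matches the stated 81.48%.
- Goal 0.80, n = 86: r = 76. Power is 0.9185 at 0.92 and reaches the stated 93.41% at 0.923.

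The text of Section 2.5 is not visible, so the true rates 0.80 and 0.923 are back-solved. These figures confirm the test; they say nothing about the endpoint definition.

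**2. Pass marks for the safety co-primary (goal 0.80).**
- n = 86: 76 successes pass (lower bound 0.8107); 75 fail (0.7972). At most 10 failures.
- n = 102: 89 pass (0.8050); 88 fail (0.7938). At most 13 failures.

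**3. Effect of k released early deaths.** Number of other failures allowed:

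| Start n | k | Deaths are failures | Deaths excluded | Deaths are successes |
|---|---|---|---|---|
| 86 | 1 | 9 | 10 | 10 |
| 86 | 2 | 8 | 10 | 10 |
| 86 | 3 | 7 | 10 | 10 |
| 102 | 1 | 12 | 13 | 13 |
| 102 | 2 | 11 | 13 | 13 |
| 102 | 3 | 10 | 12 | 13 |

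At the margin, one death can decide the test.

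**4. Chance of passing.** Let q be the share of subjects who die early and are released by the clause. The documents give no value; I take 1%, 2% and 3%. Set the success rate with all such deaths as failures at exactly 0.80.
- Deaths as failures: P(X ≥ r | n, 0.80).
- Deaths as successes: P(X ≥ r | n, 0.80 + q).
- Deaths excluded: M ~ Bin(n, 1 − q) subjects remain, each a success with probability 0.80/(1 − q), that is 0.808, 0.816 or 0.825. Average P(X ≥ r(m) | m, 0.80/(1 − q)) over M.

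| n | q | Failures | Excluded | Successes |
|---|---|---|---|---|
| 86 | 1% | 0.0298 | 0.0482 | 0.0483 |
| 86 | 2% | 0.0298 | 0.0745 | 0.0758 |
| 86 | 3% | 0.0298 | 0.1081 | 0.1153 |
| 102 | 1% | 0.0386 | 0.0612 | 0.0639 |
| 102 | 2% | 0.0386 | 0.0863 | 0.1017 |
| 102 | 3% | 0.0386 | 0.1185 | 0.1552 |

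Before rounding to four places, the excluded values for n = 86, q = 2% and n = 102, q = 3% are 0.07448 and 0.11848, hence 7.4% and 11.8% in the text. Exclusion costs nearly as much as scoring the deaths as successes at n = 86, and somewhat less at n = 102.

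**The case against.** **The default is strict.** Every early death counts by timing alone, and release needs positive evidence. CEC adjudication is explicit for the same definition in Table 2 and appears to apply in Table 1. Nothing says that a procedure-caused death is not lesion related, so the CEC could keep it in. It is also open whether the release clause governs all limbs or only the last. This stands. The finding is that the text leaves the question open, and a reader who infers that the plan drops procedural deaths as a rule goes beyond it.

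**Such a death is not usually a success.** A reader might infer that a fatal procedure scores as a safety success. Section 5.1 does not normally give that result: the subject leaves the denominator. Success would need an unusual route, such as an in-hospital death after a visit at or after day 30, a one-month visit before day 30 (the ideal window is days 23 to 44) accepted as the 30-day visit, or a reading of the Section 5.1 exception that admits subjects because they achieved technical success. This stands, but exclusion still favours the device.

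**Other rows catch some deaths.** Fatal bowel ischemia and stented-segment rupture remain failures. A fatal access bleed may already fail technical success if it led to corrective intervention related to delivery or withdrawal. This stands too; the cardiac example does not depend on those rows.

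**The size is assumed.** For the endpoint as the SAP defines it, the test keeps its level. The larger figures apply only if these deaths ought to be failures. At 1% and n = 86 the result, 4.8%, is still under 5%. The basis of the 80% goal is not visible, so changing the primary clause could separate the endpoint from its goal. This is a sound reason to put the sensitivity analysis first.

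**The remedy may exist already.** Clinical Protocol Sections 3.3 and 9.4, to which the SAP refers, are not in the public copy, and Section 5.6 is redacted; its contents list includes attrition and missing-data analyses. A sensitivity analysis there would not change the primary definition in Table 1.

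**Conclusion.** The point holds as a gap in definition and population. An early death shown to be not lesion related is not a Procedural Safety failure, the exit test does not require procedure-caused deaths to stay in, and Section 5.1 then normally removes the subject.

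Measured against an endpoint that counts these deaths as failures, exclusion raises the chance of passing at exactly 80% from 3.0% to between 4.8% and 10.8% at n = 86, and from 3.9% to between 6.1% and 11.8% at n = 102, for assumed shares of 1% to 3%. The nominal 5% is exceeded from 2% at n = 86 and from 1% at n = 102. These figures need the share to be both procedure-caused and actually released, which the documents neither state nor rule out.

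The documents do not support the stronger claims that procedural deaths are removed by rule or ordinarily scored as successes. The change is worth making before the analysis, because a test against a fixed goal should not turn on an undefined term.

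**What to change.** 1. Unless the redacted Section 5.6 already has it, pre-specify a sensitivity analysis of the first co-primary endpoint that keeps every in-hospital or 30-day death in the Section 5.1 population and counts it as a failure. This leaves the primary endpoint and its goal as they are.
2. State in Table 1 that a death the CEC finds related to the procedure or the device is not released by the lesion-related clause. First check that this matches the mortality definition behind the 80% goal.

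The cost is one table and one clause. No new data collection is evident, since the default rule already requires these deaths to be identified. The reported success rate may be slightly lower.
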